### 9.2.3.3 BSI/Sepsis

- **Sustained Clinical Cure:** Continued resolution or substantial improvement of baseline signs and symptoms associated with reduction in SOFA score, such that no antibacterial therapy is required for the treatment of the subjects original BSI/sepsis in a subject assessed as cured at TOC.
- **Relapse:** Recurrence of signs and/or symptoms of BSI/sepsis, or appearance of new signs and/or symptoms of the subjects original BSI/sepsis or death due to BSI/sepsis in a subject assessed as cured at TOC.
- **Indeterminate:** Lost to follow-up due to death other than BSI/sepsis at Days 1, 2 or 3, withdrawal, no assessment, or received additional antibacterial therapy more than 48 hrs between TOC and FU for the treatment of the current infection.
- **Clinical Failure:** Clinical failure at TOC will be carried forward.

## 9.2.4 Microbiological Outcomes per Baseline Pathogen for EOT and TOC

The microbiological outcomes per baseline pathogen will be determined by the sponsor according to the following criteria established for each infection site at EOT and TOC.

### 9.2.4.1 HABP/VABP/HCABP

- **Eradication:** Absence of the baseline Gram-negative pathogen from an appropriate clinical specimen. If it is not possible to obtain an appropriate clinical culture and the subject has a successful clinical outcome, the response will be presumed to be eradication. In the case of BSI, if the subject has a successful clinical outcome and the investigator considers no further need to obtain a clinical culture, the response will be presumed to be eradication.
- **Persistence:** Continued presence of the baseline Gram-negative pathogen from an appropriate clinical specimen or death due to pneumonia. If EOT is persistence, TOC is also persistence.
- **Indeterminate:** Lost to follow-up due to death not related to current infection, withdrawal, no assessment, or additional antibacterial therapy for the treatment of the current infection.

#### 9.2.4.2 cUTI

- **Eradication:** A urine culture shows the baseline Gram-negative uropathogen found at entry at  $\geq 10^5$  CFUs/mL are reduced to  $< 10^3$  CFUs/mL.
- **Persistence:** A urine culture shows that the baseline Gram-negative uropathogen found at entry at  $\geq 10^5$  CFUs/mL grows  $\geq 10^3$  CFUs/mL or death due to cUTI. If EOT is persistence, TOC is also persistence.
- **Indeterminate:** Lost to follow-up due to death not related to current infection, withdrawal, no assessment, or additional antibacterial therapy for the treatment of the current infection.

#### 9.2.4.3 BSI/Sepsis

- **Eradication:** Absence of the baseline Gram-negative pathogen from a blood culture and/or other primary source as applicable. If the subject has a successful clinical outcome and it is not possible to obtain an appropriate clinical culture, the response will be presumed to be eradication. In the case of BSI, if the subject has a successful clinical outcome and the investigator considers no further need to obtain a clinical culture, the response will be presumed to be eradication.
- **Persistence:** Continued presence of the baseline Gram-negative pathogen from a blood culture or other primary source or death due to BSI/sepsis. If EOT is persistence, TOC is also persistence.
- **Indeterminate:** Lost to follow-up due to death not related to current infection, withdrawal, no assessment, or additional antibacterial therapy for the treatment of the current infection.

### 9.2.5 Microbiological Outcomes per Baseline Pathogen for Follow-up

Microbiological outcomes by baseline pathogen will be determined by the sponsor according to the following criteria established for each infection site at FU.

#### 9.2.5.1 HABP/VABP/HCABP

- **Sustained Eradication:** Absence of the baseline Gram-negative pathogen from an appropriate clinical specimen after TOC. If it is not possible to obtain an appropriate clinical culture and the subject has a successful clinical response after TOC, the response will be presumed eradication.
- **Recurrence:** Recurrence of the baseline Gram-negative pathogen from an appropriate clinical specimen taken after TOC and the TOC culture is negative or death due to pneumonia.
- **Indeterminate:** Lost to follow-up due to death not related to current infection, withdrawal, no assessment, or additional antibacterial therapy for the treatment of the current infection.
- **Persistence:** Persistence at TOC will be carried forward.

#### 9.2.5.2 cUTI

- **Sustained Eradication:** A culture taken any time after documented eradication at TOC, and a urine culture obtained at FU shows that the baseline uropathogen found at entry at  $\geq 10^5$  CFUs/mL remains  $< 10^3$  CFUs/mL.
- **Recurrence:** A culture taken any time after documented eradication at TOC, up to and including FU that grows the baseline uropathogen  $\geq 10^3$  CFUs/mL or death due to cUTI.
- **Indeterminate:** Lost to follow-up due to death not related to current infection, withdrawal, no assessment, or additional antibacterial therapy for the treatment of the current infection.
- **Persistence:** Persistence at TOC will be carried forward.

#### 9.2.5.3 BSI/Sepsis

- **Sustained Eradication:** Absence of the baseline Gram-negative pathogen from a blood culture or other primary source after TOC as applicable. In the case of sepsis, if the subject has a successful clinical outcome after TOC and it is not possible to obtain an appropriate clinical culture, the response will be presumed to be sustained eradication. In the case of BSI, if the subject has a successful clinical outcome and the investigator considers no further need to obtain a clinical culture, the response will be presumed to be eradication.
- **Recurrence:** Recurrence of the baseline Gram-negative pathogen from a blood culture or other primary source after TOC and the TOC culture is negative or death due to BSI/sepsis.
- **Indeterminate:** Lost to follow-up due to death not related to current infection, withdrawal, no assessment, or additional antibacterial therapy for the treatment of the current infection.
- **Persistence:** Persistence at TOC will be carried forward.

#### 9.2.6 Per Subject Microbiological Outcomes

As shown in [Table 9-1](#), subjects who experience eradication of all baseline Gram-negative pathogens at EOT and TOC will be considered “eradication” and subjects who experience persistence of any baseline Gram-negative pathogen will be considered “persistence.” Subjects whose experiences are other than above will be considered “indeterminate.” At FU, subjects who experience sustained eradication of all baseline Gram-negative pathogens after documented eradication at the TOC will be considered “sustained eradication” and subjects who experience persistence or recurrence of any baseline Gram-negative pathogen or subjects who are considered as “persistence” at TOC will be “persistence.” Subjects whose experiences are other than above will be considered “indeterminate.”

### 9.3 Primary Efficacy Endpoint

The primary endpoints in subjects with HABP/VABP/HCABP or BSI/sepsis and in subjects with cUTI are the following:

- For subjects with HABP/VABP/HCABP or BSI/sepsis, clinical outcome per subject at TOC.
- For subjects with cUTI, microbiologic outcome (for Gram-negative pathogen) per subject at TOC.

### **9.3.1 Primary Analyses for the Primary Efficacy Endpoint**

For the CR Micro-ITT population, the following analysis will be performed.

The clinical outcomes at TOC will be summarized and clinical cure rates and its 95% CIs will be calculated by treatment group (cefiderocol or BAT) for subjects with HABP/VABP/HCABP or BSI/sepsis, separately. The clinical response rate will be calculated as the proportion of subjects whose clinical outcome is clinical cure at TOC.

The microbiological outcomes at TOC will be summarized and microbiological eradication rates and its 95% CIs will be calculated by treatment group (cefiderocol or BAT) for the subjects with cUTI. The microbiological response rate will be calculated as the proportion of subjects whose all of baseline Gram-negative uropathogen(s) are eradicated at TOC.

### **9.3.2 Supplementary Analyses for the Primary Efficacy Endpoint**

#### **9.3.2.1 Supplementary Analyses for the Primary Efficacy Endpoint Using Different Population**

For the CR-ME population and Micro-ITT population, the primary analyses stated in Section 9.2.1 will be performed as supplementary analyses.

#### **9.3.2.2 Supplementary Analyses for the Microbiological Outcome Changing Eradication Criteria for cUTI**

For the subjects with cUTI in the CR Micro-ITT population, CR-ME population and Micro-ITT population based on the definition of microbiological outcomes below, the outcomes at each time point will be summarized and its 95% CIs will be calculated by treatment group.

For EOT and TOC:

- **Eradication:** A urine culture shows the baseline Gram-negative uropathogen found at entry at  $\geq 10^5$  CFUs/mL are reduced to  $< 10^4$  CFUs/mL.
- **Persistence:** A urine culture shows that the baseline Gram-negative uropathogen found at entry at  $\geq 10^5$  CFUs/mL grows  $\geq 10^4$  CFUs/mL.
- **Indeterminate:** No urine culture obtained or additional antibacterial therapy for the treatment of the current infection.

For FU:

- **Sustained Eradication:** A culture taken any time after documented eradication at TOC, and a urine culture obtained at FU shows that the baseline uropathogen found at entry at  $\geq 10^5$  CFUs/mL remains  $< 10^4$  CFUs/mL.
- **Recurrence:** A culture taken any time after documented eradication at TOC, up to and including FU that grows the baseline uropathogen  $\geq 10^4$  CFUs/mL.
- **Indeterminate:** No urine culture or subject received additional antibacterial therapy for the treatment of the current infection. Indeterminate at TOC will be carried forward.
- **Persistence:** Persistence at TOC will be carried forward.

### 9.3.3 Subgroup Analyses

Clinical outcome and microbiological outcome per subject at TOC will be summarized by age group, gender, race, and infection site, type of baseline CR pathogen, APACHE II score ( $\leq 15$  and  $\geq 16$ ), and region (North America, South America, Europe, and Asia-Pacific) for the CR Micro-ITT population. The same analysis will be applied for microbiological outcome, and 28 days all-cause mortality.

Other subgroup analyses may be performed if deemed necessary.

## 9.4 Secondary Endpoints

The secondary endpoints of this study are the following:

- Clinical outcome per subject at EOT and FU (HABP/VABP/HCABP or BSI/sepsis)
- Clinical outcome per pathogen at EOT, TOC, and FU (HABP/VABP/HCABP, BSI/sepsis or cUTI)
- Clinical outcome per subject/pathogen at EOT, TOC, and FU (cUTI)
- Clinical outcome per subject/pathogen at EOT, TOC, and FU (HABP/VABP/HCABP + BSI/sepsis, overall)
- Clinical outcome per CR pathogen at EOT, TOC, and FU (HABP/VABP/HCABP, BSI/sepsis, cUTI, HABP/VABP/HCABP + BSI/sepsis, overall)
- Microbiological outcome (for baseline Gram-negative pathogens) per subject/pathogen at EOT, TOC, and FU (HABP/VABP/HCABP or BSI/sepsis)
- Microbiological outcome (for baseline Gram-negative pathogens) per subject at EOT and FU (cUTI)
- Microbiological outcome (for baseline Gram-negative pathogens) per pathogen at EOT, TOC, and FU (cUTI)
- Microbiological outcome (for baseline Gram-negative pathogens) per subject/pathogen at EOT, TOC, and FU (HABP/VABP/HCABP + BSI/sepsis, overall)

- Microbiological outcome (for baseline CR Gram-negative pathogens) per subject at EOT, TOC and FU (HABP/VABP/HCABP, BSI/sepsis, cUTI, HABP/VABP/HCABP + BSI/sepsis, overall)
- Microbiological outcome (for baseline CR Gram-negative pathogens) per pathogen at EOT, TOC, and FU (HABP/VABP/HCABP, BSI/sepsis, cUTI, HABP/VABP/HCABP + BSI/sepsis, overall)
- Microbiological outcome with documented carbapenem-resistant Gram-negative bacteremia (overall) at EOT, TOC, and FU
- Composite clinical and microbiological outcome at EOT, TOC, and FU (HABP/VABP/HCABP, BSI/sepsis, cUTI)
- All-cause mortality at Day 14 and Day 28
- Composite endpoint of survival and no change in antibiotic treatment due to either lack of therapeutic benefit or drug-related toxicity at TOC
- Survival time (HABP/VABP/HCABP, BSI/sepsis)
- CPIS parameters at EOT, TOC, and FU (HABP/VABP/HCABP only)
- SOFA score at EOT, TOC, and FU

#### **9.4.1 Analyses for Secondary Efficacy Endpoints**

The following analyses of the secondary efficacy endpoints will be performed for the CR Micro-ITT population.

##### **9.4.1.1 Clinical Outcome**

For the clinical outcome per subject, the outcomes will be summarized and the cure rate and its 95% CI at EOT, TOC (only for cUTI) and FU will be calculated by treatment group per infection site (HABP/VABP/HCABP, cUTI, and BSI/sepsis). The clinical response rate will be calculated as the proportion of subjects whose clinical outcome is clinical cure at each point. In addition, the clinical outcome per subject for HABP/VABP/HCABP + BSI/sepsis and overall will be analyzed in a similar manner. For Micro-ITT, CR-MITT2 and CR-ME population, same analysis will be applied.

In addition, the outcomes will be summarized and the cure rate at TOC will be calculated by treatment group per study drug regimen and antibacterial treatment regimen at Day 1 and Day 2.

For the clinical outcome per pathogen, the outcomes will be summarized and the cure rate and its 95% CI at EOT, TOC and FU will be calculated by treatment group per infection site. In addition, the clinical outcome per subject for HABP/VABP/HCABP + BSI/sepsis and overall will be analyzed in a similar manner. Clinical outcome per CR pathogen will also be summarized. For the CR-MITT2 population, the same analysis will be applied.

In addition to the analyses described above, the clinical cure rate per pathogen at TOC will also be tabulated by the MIC values and susceptibility defined by CLSI of the

baseline pathogen. For this analysis, MIC for cefiderocol, amikacin, aztreonam, ceftazidime-avibactam, meropenem, ceftolozane-tazobactam, ciprofloxacin, imipenem, cefepime, colistin, and tigecycline. For European Medicines Agency (EMA), the same analysis will be performed with the susceptibility defined by EUCAST.

#### **9.4.1.2 Microbiological Outcome**

For the microbiological outcome per subject, the outcomes will be summarized and the eradication rate with 95% CI by treatment group per infection site at EOT, TOC (only for HABP/VABP/HCABP and BSI/sepsis) and FU will be calculated. The eradication rate is the proportion of subjects whose all of baseline Gram-negative pathogen(s) are eradicated at each time point. In addition, the microbiological outcome per subject for HABP/VABP/HCABP + BSI/sepsis and overall will be analyzed in a similar manner. For Micro-ITT, CR-MITT2 and CR-ME population, same analysis will be applied.

In addition, the outcomes will be summarized and the cure rate at TOC will be calculated by treatment group per study drug regimen and antibacterial treatment regimen at Day 1 and Day 2.

For the microbiological outcome per subject with documented carbapenem-resistant Gram-negative bacteremia at baseline, the outcomes will be summarized and the eradication rate with 95% CI by treatment group at EOT, TOC and FU will be calculated as the proportion of subjects who have documented carbapenem-resistant Gram-negative bacteremia at baseline to subjects who experience eradication of baseline documented carbapenem-resistant Gram-negative bacteremia. For this analysis, the same criteria of 9.2.4.3 and 9.2.5.3 will be used but only considering blood sample.

For the microbiological outcome per pathogen, the outcomes will be summarized and the eradication rate with 95% CI will be calculated per infection site by treatment group at EOT, TOC and FU will be calculated. The microbiological outcome per pathogen only including baseline carbapenem-resistant pathogen will also be summarized. For the CR-MITT2 population, the same analysis will be applied.

In addition to the analyses described above, the eradication rate per pathogen at TOC will also be tabulated by the MIC values and susceptibility defined by EUCAST of the baseline pathogen. For this analysis, MIC for cefiderocol, amikacin, aztreonam, ceftazidime-avibactam, imipenem, ceftolozane-tazobactam, ciprofloxacin, meropenem, cefepime, colistin, and tigecycline.

For supplementary analysis, the eradication rate, defined in Section 9.3.2, per pathogen at TOC will also be tabulated by the MIC values and susceptibility defined by CLSI.

Super infections caused by a Gram-negative pathogen will be summarized and tabulated by the MIC values and susceptibility. Earliest MIC data for each super infection will be used for the analysis.

#### **9.4.1.3      Supplementary Clinical Outcomes**

For the supplementary clinical outcome per subject, the outcomes will be summarized and the cure rate and its 95% CI at EOT, TOC and FU will be calculated by treatment group per infection site (HAP/VAP/HCAP, cUTI, BSI/sepsis, HAP/VAP/HCAP plus BSI/sepsis and overall). The clinical response rate will be calculated as the proportion of subjects whose clinical outcome is clinical cure at each point. For Micro-ITT population, the same analysis will be applied.

In addition, the outcomes will be summarized and the cure rate at TOC will be calculated by treatment group per study drug regimen and antibacterial treatment regimen at Day 1 and Day 2.

For the clinical outcome per pathogen, the outcomes will be summarized and the cure rate at EOT, TOC and FU will be calculated by treatment group. The clinical response rate will be calculated as the proportion of subjects whose clinical outcome is clinical cure at each point. Supplementary clinical outcome per CR pathogen will also be summarized.

#### **9.4.1.4      Supplementary Microbiological Outcomes**

For the supplementary microbiological outcome per subject, the outcomes will be summarized and the microbiological eradication rate and its 95% CI at EOT, TOC and FU will be calculated by treatment group per infection site (HAP/VAP/HCAP, cUTI, BSI/sepsis, HAP/VAP/HCAP plus BSI/sepsis and overall). The supplementary microbiological eradication rate will be calculated as the proportion of subjects whose supplementary microbiological outcome is microbiological eradication at each point. For Micro-ITT population, same analysis will be applied.

In addition, the outcomes will be summarized and the eradication rate at TOC will be calculated by treatment group per study drug regimen and antibacterial treatment regimen at Day 1 and Day 2.

For the supplementary microbiological outcome per pathogen, the outcomes will be summarized and the eradication rate at EOT, TOC and FU will be calculated by treatment group. The eradication rate will be calculated as the proportion of subjects whose microbiological outcome is eradication at each point.

The supplementary microbiological outcome per pathogen only including baseline carbapenem-resistant pathogen will also be summarized.

#### **9.4.1.5      Composite Outcome**

For the composite clinical and microbiological outcome, the outcomes will be summarized and the response rate with 95% CI at EOT, TOC, and FU will be calculated per infection site by treatment group as the proportion of subjects who have both clinical cure and microbiological eradication.

#### **9.4.1.6 All-cause Mortality and Survival Time**

All-cause mortality rate with 95% CI at Day 14, Day 28 and overall by treatment group will be calculated as the proportion of subjects who experienced mortality regardless of the cause at or before Day 14 and Day 28, respectively. In this analysis, deaths occurring after EOS will not be used for analysis and any subject who does not have vital status information at Day 14 and 28 will not be included in the analysis. This analysis will be performed for both CR MITT and ITT Population.

In addition, for CR MITT Population, subgroup analysis regarding all-cause mortality at Day 28 will be performed. For the survival time up to End of Study (EOS), the survival curve using Kaplan-Meier method by treatment group will be presented. For the subjects whose vital status is survival at EOS, the subjects will be treated as right-censored at EOS. For the subjects whose vital status is not collected or unknown, the subjects will be treated as right-censored at last visit day.

All-cause mortality rate at Day 14, Day 28 and overall including death after EOS will be calculated by treatment group for ITT population.

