3.0	27 Jun 2019	[REDACTED]	

▪ Add time imputation for lab data and microbiological data if time is missing (section 6.4.1 and 6.4.2)

▪ Add CR MITT 2 Population (section 5.3.1) and analysis using CR MITT2 (section 7.1, 9.4.1.1 and 9.4.1.2)

▪ Add data handling for subject who receive cefiderocol after BAT completion (section 5.5 and 10.1.1)

▪ Add analysis window for premature EOT

▪ Differentiate persistence and recurrence which was originally counted together (section 9.1.6) and update table 9-3

▪ Add overall mortality until EOS. In addition, add overall mortality including death after EOS. (section 9.4.1.6)

▪ Add analysis for fatal AE (section 10.1)

▪ Clarify if investigator consider BSI subject as clinically cured and no need to collect blood sample, considered as presumed eradication (section 9.1.3.3 and 9.1.4.3)

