#### **6.4.2 Missing Microbiological or Clinical Outcome**

For clinical and microbiological outcomes, subjects who are lost to follow-up or have missing or "indeterminate" outcomes will be included in the denominator as indeterminate for cure/eradication rate, i.e., considered as not responders. If judged by the investigator that a subject died due to pneumonia, BSI/sepsis or cUTI, the clinical outcome will be considered as clinical failure after the event of death. If a subject died due to other reasons, the clinical outcome will be considered as "indeterminate" after death.

For clinical outcome, if a subject received additional antibiotics for target disease (i.e., baseline infection) before the target date, the outcome will be considered as "clinical failure". If a subject did not receive additional antibiotics for target disease before the target date, the outcome will be considered as "indeterminate".

Missing values for other individual data points will remain as missing unless otherwise specified. All analysis will be based on observed case unless otherwise stated.

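### Overall mortality is a crude proportion counted to each subject's own End of Study, so it does not compare the arms over a common period; the Day 14 and Day 28 rates are complete-case (minor)

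*SAP*

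**What the plan says.** SAP 9.4.1.6 defines the estimator: "All-cause mortality rate with 95% CI at Day 14, Day 28 and overall by treatment group will be calculated as the proportion of subjects" who died from any cause at or before Day 14 and Day 28 respectively. That definition gives no day for the overall figure. The cut-off comes from the next sentence, "deaths occurring after EOS will not be used for analysis", and from the version 3.0 entry in the SAP's Records on Revisions: "Add overall mortality until EOS. In addition, add overall mortality including death after EOS". So 'overall' is a time horizon that ends at EOS and not a pooling over infection sites. SAP 9 makes Clopper-Pearson the default interval for a proportion, and that interval takes no account of follow-up time.

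Protocol 3.1 and Table 7-2 put EOS at EOT + 28 days, ± 3 days. Protocol 5.2 expects 7 to 14 days of treatment, extendable to 21, with 5 days allowed in cUTI only. Under Protocol Appendix 1 (footnote c), EOT can fall at any time after one dose.

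For missing status, SAP 9.4.1.6 says that "any subject who does not have vital status information at Day 14 and 28 will not be included in the analysis". This agrees with the default in SAP 6.4.2: "All analysis will be based on observed case unless otherwise stated". The Kaplan-Meier curve in the same section handles it differently: "For the subjects whose vital status is not collected or unknown, the subjects will be treated as right-censored at last visit day". A further table has no stated last day: "All-cause mortality rate at Day 14, Day 28 and overall including death after EOS will be calculated by treatment group for ITT population".

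**The concern.** A row headed overall mortality, shown by arm with a 95% CI, invites the reading that both arms were observed for the same time. They were not, unless treatment durations match. The window moves one-for-one with EOT, which is a post-randomisation event decided by the investigator in an open-label trial. It is also partly driven by outcome: under Protocol 6.2.4, an antibiotic may be added or substituted only after an assessed failure, and that brings an EOT assessment. Subjects who fail early can therefore have the shortest window, and subjects on extended treatment the longest. Following discontinued patients to EOS (Protocol 7.13) does not remove this, because their EOS moves with their EOT.

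The Day 14 and Day 28 rates have fixed ends, but they keep known deaths and discard the follow-up of subjects lost while alive. That pushes the rate up slightly even when loss has nothing to do with death. What is at stake is how two descriptive rows are read.

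**Working it through.** **Reproducing the plan's own figure.** EOS day = EOT day + 28. 7 + 28 = 35 days (5.0 weeks) and 21 + 28 = 49 days (7.0 weeks), which matches the 5 to 7 weeks of participation in Protocol 3.3.1.

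**Window by EOT day**

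| EOT | Nominal EOS | With ± 3 days |
|---|---|---|
| Day 1 | 29 | 26–32 |
| Day 5 | 33 | 30–36 |
| Day 7 | 35 | 32–38 |
| Day 14 | 42 | 39–45 |
| Day 21 | 49 | 46–52 |

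**Assumptions.** The documents give no mortality, hazard or loss figure. I take Day 28 mortality m of 20% or 30% and S(t) = exp[ln(1 − m) × (t/28)^k], where k = 1 is a constant hazard (upper case) and k = 0.6 has deaths concentrated early.

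**Effect of the window on the overall figure.** With m = 20% and k = 0.6, 1 − S(t) is 20.4% at Day 29, 21.8% at Day 33, 22.5% at Day 35, 24.8% at Day 42 and 26.8% at Day 49. Now give both arms the same mortality curve and let mean EOT differ by d days. The shift is S(39 − d/2) − S(39 + d/2):

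| m | k | d = 1 | d = 2 |
|---|---|---|---|
| 20% | 0.6 | 0.32 | 0.64 |
| 30% | 0.6 | 0.43 | 0.87 |
| 20% | 1 | 0.58 | 1.17 |
| 30% | 1 | 0.78 | 1.55 |

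The range is about 0.3 to 1.6 percentage points.

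For early stopping, suppose one arm has 10 points more subjects with EOT on Day 5 instead of Day 11, with a late hazard of 0.4% per day and 80% alive at Day 28. Those subjects are observed for 5 rather than 11 days beyond Day 28: 0.80 × 0.10 × [(1 − e^(−0.004×11)) − (1 − e^(−0.004×5))] = 0.19 points. At 20 points more it is 0.37.

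**Complete-case rates.** Let A = P(death by day T, before loss) and B = P(alive and not lost at T). The reported rate tends to A/(A + B). With m = 20%, exponential loss of 5% by Day 28 and k = 1: A = 0.1951, B = 0.80 × 0.95 = 0.760, and A/(A + B) = 20.43%, which is 0.43 points too high.

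| Loss by Day 28 | Day 28 excess, k = 1 | Day 28 excess, k = 0.6 |
|---|---|---|
| 2% | 0.17 | 0.21 |
| 5% | 0.43 | 0.54 |
| 10% | 0.90 | 1.12 |

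If exclusion is per time point, the Day 14 excess is at most 0.40 points at 10% loss. Between arms the Day 28 excess cancels when loss is equal. It leaves 0.26 to 0.33 points for 2% against 5% loss, and 0.47 to 0.58 for 5% against 10%.

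Loss that is related to death is a different problem, and Kaplan-Meier does not repair it. With 50 BAT subjects, 10 known deaths and 2 unknown, the complete-case rate is 10/48 = 20.8%, and the possible range is 10/50 = 20% to 12/50 = 24%.

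**Against sampling error.** 10 deaths in 50 has a Clopper-Pearson interval of 10.0% to 33.7%. For about 100 against 50 subjects at 20% mortality, the 95% half-width of the difference is 1.96 × √(0.16/100 + 0.16/50) = 13.6 points.

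**The case against.** The overall figure is an added descriptive row. The objectives and the listed secondary endpoints name mortality at Day 14 and Day 28 only, and SAP 6.2 attaches no test to mortality. The same section already plans fixed-day rates and a Kaplan-Meier curve to EOS, which is the usual way to handle unequal follow-up. Both arms share the same expected duration, and nothing in the documents shows that EOT will differ between them. Missing status is limited by follow-up after discontinuation (Protocol 7.13) and by allowing EOS by phone (Protocol 8.5). All of this stands, and it keeps the point minor.

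A reader might infer three stronger things.

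- *That overall mortality will be materially biased between arms.* Counting the same risk to Day 35 and to Day 49 does give gaps of 2.2 to 8.0 points at 20% Day 28 mortality, when the hazard after Day 28 is 25 to 100% of a constant earlier hazard. But that sets everyone at 7 days against everyone at 21 days, and the documents give no reason to expect such a contrast between arms.
- *That the plan leaves it open whether cUTI is included.* SAP 9.4 restricts one item to two sites, "Survival time (HABP/VABP/HCABP, BSI/sepsis", lists mortality without restriction, and SAP 15 adds cUTI to mortality. The natural reading is that the mortality rates include cUTI and the survival curve does not. What remains is that the two cover different subjects.
- *That exclusion for unknown status is wholly undefined.* The word 'respectively' in the definition supports handling per time point. One sentence would settle it.

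A fair caution applies to the remedy. A Day 35 estimate does not fully escape dependence on EOT, because some subjects reach EOS before Day 35. Day 28 is the sounder main horizon.

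**Conclusion.** The point holds as a minor one. Overall mortality in SAP 9.4.1.6 is a crude proportion over subject-specific windows set by treatment duration, so it compares the arms over a common period only if duration and early stopping are alike. The likely shift is about 0.3 to 1.6 points for a 1- or 2-day difference in mean EOT. The Day 28 complete-case excess is about 0.2 to 1.1 points within an arm and less between arms. These sizes rest on assumed mortality of 20 to 30% (20% for the complete-case part), the two hazard shapes above, and 2 to 10% loss unrelated to death. All are small beside sampling error. Because mortality is secondary and untested, and fixed-day rates stand beside the overall row, the risk is misreading and not a wrong formal conclusion.

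**What to change.** 1. Keep Day 28 as the main common horizon. Tabulate Kaplan-Meier mortality with 95% CI at Day 14 and Day 28 for CR Micro-ITT and ITT, on the same infection sites as the mortality table, including cUTI.
2. Beside or instead of the crude overall row, give Kaplan-Meier mortality at one later prespecified day, for example Day 35 (nominal EOS for a 7-day course), with numbers at risk and numbers censored earlier by arm. State that subjects with EOT before Day 7 (nominal EOS Day 29 to 34), and those with EOT on Day 7, 8 or 9 and an early EOS visit (Day 32, 33 or 34 at the earliest), may be censored before Day 35, and that this censoring may be informative.
3. If the crude overall row stays, label it as running to each subject's own EOS and not as a common-period comparison.
4. Keep the complete-case rates, state that exclusion is per time point, and add counts of unknown vital status by arm with best- and worst-case bounds.
5. State the last day covered by the ITT table that includes deaths after EOS.

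The cost is SAP wording, a few table rows and one more Kaplan-Meier run for ITT and to bring in cUTI. No new data are needed.
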